After children and parents complete assent and consent forms, they will be asked to complete all survey measures including demographics, household composition, physical activity and eating habits, screen use, puberty stage, overconcern with weight or shape, school grades, and psychosocial measures. Children and parents will be encouraged to complete online REDCap surveys on separate devices. The research coordinator will review all surveys for completeness before ending the call. Parents will be asked to schedule a second zoom call within the upcoming 3 weeks. An electronic cellular-connected scale (BodyTrace), a tape measure to measure height, and a food portion size booklet to use during the dietary recall will be mailed to participants. Parents will be emailed a lab requisition for their child to have fasting blood tests collected at their local Quest labs.

Measures in baseline appointment – part 2

During the second Zoom video appointment, child's and parent's heights and weights will be measured using the mailed tape measure and electronic scale, and children will complete a 24-hour dietary recall. Child weight measurements will be used to determine child's eligibility into the study (≥ 95 th BMI percentile for age and sex). After finalizing eligibility and completing all baseline measures, participants will be randomized.

Randomization:

Families will be randomized to treatment conditions after completing baseline measures, using Efron's biased coin randomization stratified by location, sex, and race/ethnicity, to promote balance on key characteristics that may influence weight changes, and allow examination of sex as a biological variable. Investigators and all data collection staff will

remain blinded to treatment condition assignment until all participants have completed the final follow-up assessments.

Interventions:

The research activities will be delivered as online videos and activities sent 9 times throughout the program. Parents will be emailed REDCap surveys that link to Qualtrics activities; one with a parent video/activity and one with a child video/activity. The WISE interventions encourage values affirmations and a growth mindset. The control videos and activities reinforce diet and physical activity messages that are part of the weight control program.

Follow-up Assessments

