3. BACKGROUND

a. Past Experimental and/or Clinical Findings

Childhood obesity is a medical and public health priority. Pediatric obesity in the U.S. has more than tripled over the past 3 decades. Childhood obesity is associated with substantial medical, psychological, and social morbidities. Most treatments for children with obesity have produced modest, unsustained effects, and there remains a great need for new approaches to increase and sustain weight loss among children with obesity.

Existing weight control interventions may be limited in their success, in part, because of the many psychological barriers and threats that children and families face when attempting to manage their weights. Therefore, one potentially effective and efficient way to enhance the success of behavioral treatments and reduce variability in outcomes may be to focus on changing the attitudes and preparedness of the participants. One of the most formidable psychological barriers faced by people trying to control their weight is

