4. PARTICIPANT POPULATION

a. Planned Enrollment

(i) We expect to enroll approximately 200 families. Because multiple eligible children and parents may be enrolled from a single family, this is expected to include up to 240 eligible children and 240 eligible parents.

(ii) We are the only site involved in this research. Therefore, the total sample will be approximately 200 families.

(iii) Children aged 10-16 years with obesity and their parents/guardians. Children and their parents are included because this is a study to test a family-based approach to reduce weight gain in children with obesity using online methods.

b. Age, Gender, and Ethnic Background

Based on past experience in the existing pediatric weight control treatments, we anticipate participants to be approximately: 55% girls, 45% boys, 50% white, 3% African-American, 25% Latino/Hispanic, 1% Native American, 8% Asian/Pacific Islander and 13% other (including multi-ethnic).

c. Vulnerable Populations

Up to approximately 240 10-16 year-old children with obesity (in 200 families).

Rationale for Involvement of Potentially Vulnerable Subjects.

Children with obesity are at increased risk of related morbidities, including hypertension, dyslipidemias, diabetes, non-alcoholic fatty liver disease, and atherosclerosis, among others, and future risk of heart disease, stroke and many cancers. However, most available pediatric obesity treatment programs produce only limited and non-sustained effects. There is a great need for new, innovative approaches to improve and sustain weight control among overweight and obese children. In the proposed trial, we will test the addition of several promising and potentially generalizable social psychological strategies.

To minimize risks and chance of harm, assent will be obtained from all children and consent will be obtained from parents/guardians for their child's and their own participation, after full explanation of the study, via zoom video call. Parents/guardians will be required to accompany their child during participation in the study zoom calls.

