Wise Social Psychological Interventions to Improve Outcomes of Behavioral Weight
Control in Children With Obesity

Statistical Analysis Plan

NCT04422951

May 13, 2022

Study Design: two-arm, parallel group, randomized controlled trial.

Primary Hypothesis: Compared to children randomized to receive a usual care behavioral pediatric weight management program alone, children randomized to receive a usual care behavioral pediatric weight management program plus the wise social psychological interventions will have a significantly attenuated BMI trajectory over 6 months.

Primary Outcome: Body mass index (BMI) trajectory over the 6-months duration of the study for each participant.

Primary Analysis, Statistical Model and Approach: We will use mixed effects linear regression techniques to address our aims. Such models are typically utilized in the clinical trials setting where repeated measurements are proposed.^{154,155} Specifically, we will regress BMI at a given time point on study arm, days since randomization, and an interaction between study arm and days since randomization. Also included in the model are a subject-specific random effect to account for the correlation of measurements over time within a subject and a group-specific random effect to account for the correlation among outcomes across subjects assigned to the same group and behavior coaches. Both random effects are assumed to be normally distributed. Finally, we include the randomization factors: sex and race/ethnicity. The proposed model can be expressed as:

$$\text{BMI}_{ij} = \beta_0 + \gamma_i + \delta_{j(i)} + \beta_1 \text{ treatment}_i + \beta_2 \text{ time}_{ijk} + \beta_3 \text{ treatment}_i \times \text{time}_{ijk} + \beta_4 \text{ sex}_i + \beta_5 \text{ ethnicity}_i + \varepsilon_{ijk},$$

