where ε_{ijk} is the random error term assumed to follow a normal distribution for the k^{th} observation corresponding to the i^{th} child assigned to the j^{th} group, γ_i is the subject-specific random intercept corresponding to the i^{th} child, and $\delta_{j(i)}$ is the group-specific random intercept corresponding to the j^{th} group in which the i^{th} child is nested. We are interested in drawing inference around β_3 that represents the difference in BMI trajectory over time between the two study arms. For this purpose, we will use a two-sided Wald test at the 0.05 level of significance. Our mixed effects regression approach most closely matches the study design and stratified randomization, and has advantages over a t-test endpoint analysis and other repeated measures analysis approaches for trial data including repeated measures ANOVA; it uses all available data, can accommodate differential lengths of follow-up, irregular measurement intervals, and missing data under reasonably flexible assumptions regarding the missing data mechanism.^{156,157}

Intent-to-Treat: We will adhere to intent-to-treat principles. All participants randomized will be included in the analysis and analyzed according to their original treatment assignment. While we expect limited loss to follow-up, our analysis allows subjects without complete data to be included in the analysis for their partially observed period. Such an analysis relies on a flexible assumption about missingness, namely that the data are missing related to observed features only (MAR). As a sensitivity analysis, we will also rely on multiple imputation-based methods that repeatedly impute values for those with incomplete data prior to fitting the mixed effects linear regression model. The imputation model can consider a large number of features (beyond those included in the primary analysis model). The sensitivity analysis will provide insight into the robustness of our findings to missingness and how missing data are handled.

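### The primary test is on treatment × time but the model has random intercepts only; if children's BMI slopes differ, or visit errors have positive serial correlation that fades with lag, its standard error is too small

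*SAP*

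**What the plan says.** The SAP (Primary Analysis, Statistical Model and Approach) regresses BMI on arm, days since randomization and their product, adjusted for sex and race/ethnicity. The coefficient of interest, β₃, "represents the difference in BMI trajectory over time between the two study arms". The test is fixed: "For this purpose, we will use a two-sided Wald test at the 0.05 level of significance".

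On correlation within a child the SAP says: "Also included in the model are a subject-specific random effect to account for the correlation of measurements over time within a subject". In the definitions below the equation, that term "is the subject-specific random intercept corresponding to the" child. The group term is also an intercept. The error term is described only as normal. No random slope, serial or unstructured covariance, or robust variance appears.

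Under Intent-to-Treat, the only sensitivity analysis is multiple imputation, carried out "prior to fitting the mixed effects linear regression model". As worded, that is the same model.

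The Protocol (section 2a) measures height and weight at baseline, 3 and 6 months, and states: "Families will be randomized to treatment conditions after completing baseline measures". Section 4a adds: "Because multiple eligible children and parents may be enrolled from a single family, this is expected to include up to 240 eligible children". The SAP model has no family term. The Protocol's background (section 3a) says that one way to make treatment work better and "reduce variability in outcomes may be to focus on changing the attitudes and preparedness of the participants".

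The SAP's power section claims at least 80% power for a difference of 0.4 kg/m² per 24 weeks with 80 children per arm. The inputs that it lists are sample size, retention, ICCs within individuals and within groups, BMI SDs and arm trajectories. Between-child slope variance is not listed.

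**The concern.** A constant that is common to all of a child's BMI values cancels out of that child's slope. The random intercept therefore does nothing for the standard error of β₃, which rests on the error term alone. The model in effect assumes that all children in an arm share one true slope and, on the usual reading of a single error term, that errors are independent between visits.

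If true slopes differ, the model treats the spread as visit noise. Children aged 10 to 16 in different weight management programmes are unlikely to share one slope: the Protocol gives variable outcomes as part of its rationale, and the SAP defines the primary outcome as a trajectory for each participant.

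What is at stake is the error rate of the one primary test. The p-value would be too small and the confidence interval too narrow, so ordinary differences between children in BMI change could be read as a treatment effect. No other analysis in the SAP would show this. Siblings with similar slopes would add to it.

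**Working it through.** **Inputs from the documents.** Two-sided α 0.05; three BMI values per child (baseline, 3 and 6 months); 80 per arm; difference 0.4 kg/m² per 24 weeks; power at least 80%. **Assumed, because not given:** residual SD σ (kg/m²), between-child slope SD τ (kg/m² per 24 weeks), serial correlation ρ, sibling correlation, dropout.

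**1. The plan's own figure.** Without SDs, 80% power can only be solved backwards. The required standard error is 0.4/(1.960 + 0.842) = 0.143. With 80 per arm the SD of a child's estimated slope is 0.143 × √(80/2) = 0.903, a variance of 0.815. Under the SAP model with no slope variation that variance is 2σ², so σ ≈ 0.64. This is feasible, but it cannot be confirmed.

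**2. Slope variation.** Put the visits at t = 0, 0.5, 1 in 24-week units, so the sum of squares of t about its mean is 0.5.
- True variance of a child's slope estimate: τ² + 2σ².
- Variance that the random-intercept model reports: τ²/2 + 2σ². Of the two within-child contrasts only the linear one carries τ², and the model pools both.
- R = (τ² + 2σ²)/(τ²/2 + 2σ²); actual α = 2[1 − Φ(1.96/√R)].

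Example, σ = 0.4 and τ = 0.5: R = 0.570/0.445 = 1.281, 1.96/√1.281 = 1.732, α = 8.3%. As τ grows, R tends to 2 and α to 16.6%.

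**3. A bound from the plan.** If 80% power holds with a valid standard error at 80 per arm, then τ² + 2σ² is at most 0.815. At σ = 0.4, τ² is at most 0.815 − 0.320 = 0.495, so τ is at most 0.70. Then R = 0.815/0.568 = 1.436 and α is at most 10.2%.

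| σ | α at τ = 0.25 | α at τ = 0.5 | α at τ = 1.0 | Largest τ under the bound | α at that τ |
|---|---|---|---|---|---|
| 0.3 | 6.7% | 9.9% | 13.7% | 0.80 | 12.6% |
| 0.4 | 6.0% | 8.3% | 12.2% | 0.70 | 10.2% |
| 0.5 | 5.7% | 7.4% | 11.0% | 0.56 | 7.8% |
| 0.6 | 5.5% | 6.7% | 9.9% | 0.31 | 5.7% |

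The τ = 1.0 column lies outside the bound in every row. The bound loosens with sample size: with 120 per arm (the Protocol's upper figure of 240 children) it is 13.8%, 12.0%, 10.0% and 8.1%.

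**4. Correlated visit errors, no slope variation.** For AR(1) errors with correlation ρ between adjacent visits, R = 3(1 + ρ)/(3 + ρ). At ρ = 0.5, R = 4.5/3.5 = 1.286 and α = 8.4%; at 0.3 and 0.7 it is 7.1% and 9.5%. At ρ = −0.3, α = 2.6%, which is conservative. Equal correlation between all visits is absorbed by the random intercept and leaves α at 5%.

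**5. Simulation check.** With 160 independent children, σ = 0.5 and 3,000 null trials per case, the random-intercept test rejected 7.6%, 9.6% and 11.5% at τ = 0.5, 0.75 and 1.0 (closed form 7.4%, 9.3%, 11.0%). With 20% dropout it rejected 7.3% at τ = 0.5 and 10.1% at τ = 1.0.

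**6. Does the repair work?** Here σ = 0.4, with 20,000 null trials per case and 160 children in 134 families (26 sibling pairs, assumed slope correlation 0.5). No group, sex or ethnicity terms were included. Rejection at τ = 0.25 / 0.5 / 1.0, complete visits:
- random intercept as in the SAP: 6.5 / 9.5 / 14.7%
- child random slope: 5.4 / 6.1 / 6.6%
- unstructured covariance: 5.6 / 6.2 / 6.9%
- random slope with family-clustered standard error: 5.0 / 5.2 / 5.1%
- random intercept with family-clustered standard error: 5.0 / 5.2 / 5.1%

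For AR(1) errors at 0.5 with no slope variation, the random-slope fit rejected 5.1% and the unstructured fit 5.3%.

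**7. Power with a valid standard error.** At 80 per arm and σ = 0.5, power for 0.4 is 83%, 69% and 54% at τ = 0.5, 0.75 and 1.0. At σ = 0.4 it falls below 80% once τ exceeds 0.70.

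**The case against.** The strongest objection is that the size is unknown and may be slight. The documents give neither SD, and the background remark on variable outcomes does not quantify BMI slopes. Height is read from a mailed tape measure on a video call. At an assumed BMI of 32 and height of 155 cm, a 1 cm error moves BMI by about 2 × 32/155 ≈ 0.4, so a large residual SD is plausible, and a large residual SD shrinks the inflation. At σ above about 0.64 the stated power at 80 per arm leaves no room for slope variance at all. This stands, and it limits the severity.

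A second objection is that one sentence specifying a family-clustered standard error would be enough. In the runs above it holds the level as well as the random slope does, and it avoids convergence trouble. That stands for the level of the test. It repairs only the variance, however, and leaves a covariance model that the missing-at-random argument leans on. The dropout scenarios that were run had equal dropout in both arms, so they do not settle that question.

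Several stronger readings are tempting and are not supported:
- That any correlation between visits inflates the error rate. Only positive serial correlation that fades with lag does.
- That the SAP states independent errors. It states normality; independence is the default reading.
- That the treatment estimate is biased. The fault is in its standard error.
- That the 80% power claim is wrong. The model that generated the simulated data is not shown.
- That clustering should be by treatment group with a specific small-sample rule. The documents give neither the number of groups nor whether a group contains one arm or both.
- That the sibling figures describe this trial. They use the Protocol's upper limit of 240 children and an assumed correlation.

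**Conclusion.** The concern holds in conditional form. The specified model keeps the 5% level if slopes do not vary within an arm and errors are independent or equally correlated across visits. With slope variation or fading positive serial correlation it rejects too often.

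The inflation from slope variation cannot exceed 16.6% with three complete, equally spaced visits. Over the assumed SDs it runs from 5.5% to 13.7%. If the power claim is taken at face value with a valid standard error at 80 per arm, the most it can be is between 5.7% and 12.6%, depending on residual SD. The algebra is certain; that inflation will occur, and how large it will be, is not.

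This should be fixed before analysis: it concerns the primary test, the likely direction is towards false positives, and no planned analysis would expose it. Because the effect is conditional, bounded and possibly small, it does not by itself invalidate the plan.

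**What to change.** - Add a child-level random slope for time, correlated with the random intercept, or use an unstructured covariance over the three visits. Keep the two-sided Wald test on β₃.
- Because families are randomised and siblings may enrol, take the standard error clustered by family.
- Pre-specify what counts as non-convergence, including an invalid random-effect covariance, and which fallback then applies: the unstructured covariance, or the random-intercept model with the family-clustered standard error.
- Rerun the power simulation with between-child slope variance as an input, and restate the power if it falls below 80%.

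The cost is SAP wording, a small change to the model code and one simulation rerun; no new data are needed. Intervals become somewhat wider if slopes vary, and the power figure may be less favourable. The random-slope fit can fail with three visits: in the sibling simulation it failed the covariance check in 14% of runs at slope SD 0.25 and in at most 0.2% at 0.5 or more. With the failed runs sent to the random-intercept, family-clustered test, rejection at 0.25 was 5.3%.

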Children and parents/guardians will complete data collection visits at 3 and 6 months post randomization. With the exception of demographic measures and a few baseline only measures, the 3- and 6-month visits will include measures previously collected at baseline. Fasting blood tests are included only at baseline and 6-month visits.

b. Procedure Risks

There are minimal risks in the research protocol. All research measures will be obtained by trained research assistants and phlebotomy by qualified phlebotomists at Quest Diagnostics, a nationwide commercial lab.

c. Use of Deception in the Study

There will be no deception used in the research.

d. Use of Audio and Video Recordings

No audio or video recording will occur by study staff.

As part of one of the intervention activities, children will be asked to upload a photo or a drawing to their individually assigned REDCap surveys. This image is similar to a profile image and designed to increase engagement. Children are instructed to not include photographs with faces.

Only qualified research staff will have access to images uploaded to REDCap.

e. Alternative Procedures or Courses of Treatment

No standard or alternative treatment will be withheld.

f. Will it be possible to continue the more (most) appropriate therapy for the participant(s) after the conclusion of the study?

No additional continuing treatment will be made available by the study after conclusion of the study.

g. Study Endpoint(s)

The main study endpoint is BMI change over 6 months, at the end of treatment. We do not plan to perform interim analyses of treatment

outcomes or terminate the study early for efficacy or futility because:

- Potential effects of the social psychological interventions are to
- mitigate drop out and increase perseverance with the treatment program over time.
- The interventions aim to affect weight gain trajectory and maintenance, intervention effects may not be observed over the short term.
- Alternatively, statistically significant short-term benefits may not reflect clinically significant health benefits over 6 months (the full length of the study).
- This study aims to calculate with some assurance the size of the difference between treatment outcomes (effect size) within reasonable confidence intervals, and to avoid bias in the estimates of effect sizes (because random high values in treatment effect may be used to justify early stopping, but rarely would random low values).

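### The only missing-data sensitivity analysis stays within MAR, so it cannot show robustness to missingness that depends on unobserved BMI

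*SAP*

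**What the plan says.** The SAP's Intent-to-Treat paragraph keeps every randomized participant in the analysis and lets children with incomplete follow-up contribute what was observed. It states the assumption this needs: "namely that the data are missing related to observed features only (MAR". No attrition figure is given, only "While we expect limited loss to follow-up".

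One sensitivity analysis follows: "As a sensitivity analysis, we will also rely on multiple imputation-based methods that repeatedly impute values for those with incomplete data", and then the same mixed model is fitted. The imputation model may use more variables than the primary model, but none is named. The SAP says what this is for: "The sensitivity analysis will provide insight into the robustness of our findings to missingness and how missing data are handled".

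Neither document plans a delta-adjusted, tipping-point, reference-based, pattern-mixture or selection analysis.

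Protocol section 2.g, explaining why no interim efficacy analysis is planned, lists among the potential effects of the interventions to "mitigate drop out and increase perseverance with the treatment program over time". BMI is scheduled at baseline, 3 months and 6 months (Protocol section 2.a).

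**The concern.** A sensitivity analysis for missing data is most useful when it relaxes the assumption that the primary analysis cannot check. Here both analyses assume that, given observed data, children with missing BMI resemble those who were measured. If children leave because of weight change that occurs after their last visit, both estimates can be wrong in the same direction, and similar results could be reported as robustness.

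The question has some force in this trial. An intervention meant to keep families in the weight-management program could plausibly also change who is still measured at 6 months. With only two follow-up visits, a child lost before month 3 has only a baseline BMI, so there is little observed outcome data on which MAR could rest. At stake is how far a significant or non-significant β3 can be trusted once the loss to follow-up is known.

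**Working it through.** **1. The plan's own figure.** The SAP's power section states at least 80% power for 0.4 kg/m² per 24 weeks with 80 children per arm, two-sided 0.05. It gives no SD, ICC or retention values, so the figure cannot be reproduced. Solving backwards for a simple comparison of 24-week changes with no drop-out gives the largest compatible SD of change:

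SD = 0.4 / [(1.96 + 0.842) × √(2/80)] = 0.4 / 0.443 = 0.90 kg/m².

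This SD is used below as an assumption.

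**2. Shift in the arm difference.** Let p be the share of missing 6-month values and δ the amount by which their true BMI exceeds the MAR prediction. For wise (T) minus control (C):

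shift = δT × pT − δC × pC.

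With completed data at 0, 3 and 6 months, the fitted slope per 6 months gives the three visits weights −1, 0 and +1, so a shift in the 6-month value carries straight into β3. I treat 6 months and 24 weeks as the same interval. Every p and δ is assumed. A negative difference favours wise.

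| pT, pC | δT, δC | Shift (kg/m²) | MAR estimate is |
|---|---|---|---|
| 15%, 25% | 0.5, 0.5 | 0.075 − 0.125 = −0.05 | conservative |
| 15%, 25% | 1.0, 1.0 | 0.15 − 0.25 = −0.10 | conservative |
| 20%, 20% | 0.5, 0 | +0.10 | too favourable |
| 20%, 20% | 1.0, 0 | +0.20 | too favourable |

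Against the 0.4 target, the first pair is 12.5% and 25%, and the second pair 25% and 50%. The pairs have opposite signs and should not be merged into one range.

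**3. What would overturn a result.** With SD 0.90, SE = 0.90 × √(2/80) = 0.142, and significance needs a difference beyond 1.96 × 0.142 = 0.279. An observed −0.40 therefore tolerates an unfavourable shift of 0.40 − 0.279 = 0.121. If only the wise arm departs from MAR, the tipping δ is 0.121/pT: about 1.2 at 10% missing, 0.6 at 20% and 0.4 at 30%. The SE ignores the information lost to missing data, so true tipping points would be somewhat lower.

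**4. Does the planned imputation detect the problem?** A simulation with 100,000 children per arm used mean changes of +0.6 (control) and +0.2 (wise), SD of change 0.90, BMI always seen at baseline and 3 months, and 6-month BMI missing in about 18-29% of control and 10-13% of wise children. In the informative scenarios, the log-odds of being missing changed by 1.5 per kg/m² of the unseen 6-month change. The imputation used baseline BMI, 3-month BMI and one auxiliary variable, by arm. The true difference is −0.40.

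| Missingness depends on unseen change | Primary | MAR imputation | Bias (absolute) | Bias removed |
|---|---|---|---|---|
| No | −0.404 | −0.404 | none material | – |
| Both arms, same direction | −0.307 | −0.320 | 0.093 → 0.080 | 14% |
| Wise arm only | −0.490 | −0.460 | 0.090 → 0.060 | 33% |
| Control arm only | −0.215 | −0.258 | 0.185 → 0.142 | 23% |
| Opposite directions by arm | −0.620 | −0.553 | 0.220 → 0.153 | 30% |

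The imputation moves toward the truth each time but leaves most of the bias. The gap between the two analyses is 0.013 to 0.067, less than half of the 0.142 standard error at the planned size, and would ordinarily be read as agreement.

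**The case against.** Several points on the other side are sound.

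- A reader might infer that the imputation merely repeats the primary bias. It does not. Added auxiliary variables weaken the MAR assumption, and in the simulation they removed 14-33% of the bias. The two analyses share a class of assumption, not an identical one. The SAP also promises only insight, not protection against every mechanism.
- A reader might infer that the protocol itself predicts informative, arm-dependent missingness. It does not. Section 2.g speaks of drop-out from the treatment program. BMI is measured separately by the study team over Zoom with a mailed scale and tape measure, and families receive gift cards for the 3- and 6-month assessments (Protocol section 4.j). A child can leave the program and still be measured.
- Different drop-out rates alone do not violate MAR, since arm is in the model. Dependence on unobserved BMI is also needed, and neither document asserts it.
- A reader might infer that any bias would flatter the intervention. The scenario closest to the protocol's stated aim, less drop-out in the wise arm with equal δ, makes the MAR estimate conservative.
- The documents expect limited loss, and a δ of 1.0 kg/m² exceeds the whole 0.6 kg/m² control gain in the SAP's example.

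These points limit the size and certainty of the problem. They do not supply an analysis that departs from MAR, and with no attrition figure stated, limited loss cannot be taken as given.

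**Conclusion.** The concern stands in a limited form. The planned check addresses sensitivity to extra observed variables. It does not address missingness that depends on unobserved BMI, so the SAP's robustness statement reaches further than the analysis behind it. Arm-different loss of BMI data is plausible here but not established.

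In the scenarios tried, the effect ranges from −0.10 (MAR estimate conservative) to +0.20 kg/m² (MAR estimate too favourable), against a target of 0.4. All drop-out rates, δ values and the SD of 0.90 are assumptions. If loss to follow-up proves small and balanced, the practical effect will be small, and a tipping-point analysis would show that directly. The primary analysis itself need not change; this is an inexpensive improvement to the plan.

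**What to change.** Amend the Intent-to-Treat paragraph of the SAP:

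1. Keep the MAR multiple imputation as the first step, done separately by arm, and name the auxiliary variables.
2. Pre-specify a delta-adjusted tipping-point analysis: add δ to BMI values imputed after drop-out, vary δ separately in each arm, and allow both signs. Extend the grid until the β3 conclusion changes or a stated implausible limit is reached. A limit of 1.0 kg/m² may be too narrow if only about 10% of values are missing, since the illustration above tips at about 1.2.
3. Report missing BMI by arm and visit, and the δ pairs at which the conclusion changes.
4. Optionally, add a reference-based version in which wise-arm drop-outs follow the control trajectory.
5. Limit the robustness claim for the MAR imputation to what it tests, namely sensitivity to the added variables.

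The cost is one SAP paragraph and a little programming. The sample size and primary analysis are unchanged. The downside is that the robustness statement may turn out less favourable.
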